| Activity | Screening ^a | Baseline (Week 0) | Wk 2 | Wk 4 | Wk 8 | Wk 12 | Wk 16 | Wk 20 | Wk 28 | Wk 36 | Wk 44 | Wk 52 | Early Termination (ET) Visit | Unscheduled Visit | 30-Day Follow-Up Visit |
|---|------------------------|----------------------|---------|---------|---------|----------|----------|----------|----------|----------|----------|----------|------------------------------------|----------------------|------------------------------|
| Urinalysis ^j | X | X | X | X | X | X | X | X | X | X | X | X | X | X | X |
| Pregnancy Test ^k | X | X | X | X | X | X | X | X | X | X | X | X | X | | X |
| hsCRP | X | X | X | X | X | X | X | X | X | X | X | X | X | X | X |
| HBV and HCV Screening ^l | X | | | | | | | | | | | | | | |
| ABT-494 Concentration ^m | | | X | X | X | X | X | X | X | X | X | X | X | | |
| Pharmacodynamic biomarkers | | X | | | X | | X | | | | | | X | X | |
| C. difficile toxin | X | | | | | | | | | | | | | | |
| Stool Sample (fecal calprotectin) ^{n,o} | X | | | X | | | X | | X | | | X | X | | |
| Bristol Stool Chart ^p | X | | | X | | | X | | X | | | X | X | | |
| Corticosteroid Taper ^q | | | X | | | | | | | | | | | | |
| Crohn's Disease Activity Index (CDAI) | | X | X | X | X | X | X | X | X | X | X | X | X | X | |
| Inflammatory Bowel Disease Questionnaire (IBDQ) | | X | | | X | | X | | | | | X | X | | |

Table 1. Study Activities (Continued)

| Activity | Screening ^a | Baseline (Week 0) | Wk 2 | Wk 4 | Wk 8 | Wk 12 | Wk 16 | Wk 20 | Wk 28 | Wk 36 | Wk 44 | Wk 52 | Early Termination (ET) Visit | Unscheduled Visit | 30-Day Follow-Up Visit |
|---|------------------------|----------------------|---------|---------|---------|----------|----------|----------|----------|----------|----------|----------|------------------------------------|----------------------|------------------------------|
| European Quality of Life 5 Dimensions (EQ-5D) | | X | | | X | | X | | | | | | X | X | |
| Work Productivity and Impairment Questionnaire (WPAI) | | X | | | X | | X | | | | | | X | X | |
| Abdominal Pain Rating Scale (0 – 10 Scale) | | X | | | | X | X | | | | | | | | |
| Monitor Adverse Events ^r | X | X | X | X | X | X | X | X | X | X | X | X | X | X | X |
| Study Drug Dispensing/Administration | | X | X | X | X | X | X | X | X | X | X | | | | |
| Dispense Subject Diary | X | | | | | | | | | | | | | | |
| Subject Diary Review | | X | X | X | X | X | X | X | X | X | X | X | X | X | |

Table 1. Study Activities (Continued)

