5.0 Analysis Populations

5.1 Definition for Analysis Populations

The intent-to-treat responders (ITT-R) and intent-to-treat non-responders (ITT-NR) analysis sets includes all re-randomized subjects in the double-blind extension phase and are responders and non-responders at Week 16, respectively.

For the ITT-R and ITT-NR analysis sets, subjects are assigned to a treatment group based on the re-randomization schedule, regardless of the treatment actually received. The ITT-R and ITT-NR analysis sets will be used as primary sets for all efficacy analysis. Subjects who were randomized to placebo during the Induction Period will be summarized separately.

The intent-to-treat clinical responders (ITT-CR) and intent-to-treat clinical non-responders (ITT-CNR) analysis sets includes all re-randomized subjects in the double-blind extension phase and are clinical responders and clinical non-responders at Week 16, respectively.

For the ITT-CR and ITT-CNR analysis sets, subjects are assigned to a treatment group based on the re-randomization schedule, regardless of the treatment actually received. The ITT-CR and ITT-CNR analysis sets will be used for sensitivity analysis. Subjects who were randomized to placebo during the Induction Period will be summarized separately.

The safety analysis set consists of all subjects who received at least one dose of study medication in the Extension Phase. For the safety analysis sets, subjects are assigned to a treatment group based on the treatment actually received, regardless the treatment randomized. The safety analysis set will be used for all safety analysis of Extension phase.

Any ABT-494 analysis set will consist of all subjects who received at least one dose of ABT-494 during Induction or Extension. Any ABT-494 analysis set will be used for cumulative safety analysis (from Induction baseline to study end).

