5.2 Variables Used for Stratification of Randomization

At Baseline, subjects were randomized in a 1:1:1:1:1:1 ratio to receive one of the six treatment groups (double-blind ABT-494 induction doses or matching placebo).

The following are the treatment groups:

Group 1: ABT-494 3 mg BID

Group 2: ABT-494 6 mg BID

Group 3: ABT-494 12 mg BID

Group 4: ABT-494 24 mg BID

Group 5: ABT-494 24 mg QD

Group 6: Placebo

The randomization at Baseline was stratified by endoscopic disease severity (SES-CD < 15 and \geq 15), prior anti-TNF use (naïve and experienced), and by participation in the substudy of the gene expression in intestinal biopsies (Yes and No). As part of the randomization at Baseline, subjects were randomly assigned (1:1) to have their follow-up ileocolonoscopy done at Week 12 or Week 16.

At Week 16, subjects who have completed the induction period were re-randomized in a ratio of 1:1:1 to one of the three double-blinded doses of ABT-494 3 mg BID, 6 mg BID or 12 mg BID. The re-randomization was stratified by dose received during the first 16 weeks, and overall response (responder versus non-responder) at Week 16. The subjects who were re-randomized at Week 16 to ABT-494 24 mg QD prior to Protocol Amendment 2 continued to receive the same double-blind dose until Week 52/PD.

Overall response consists of both Endoscopic response and Clinical response. The central reader endoscopic score will be used for calculating the Endoscopic response for the evaluation of the efficacy endpoints. However, for stratification re-randomization, the endoscopic score at baseline from central reader and the endoscopic score at Week 12 or Week 16 from site local reader will be used in order to determine response status.

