6.0 Analysis Conventions

Definition of Baseline for Induction Period

The Baseline visit date for Induction Period is the date when the first dose of study drug is received and referred to as Day 1 or Week 0. The Baseline value for a variable is defined as the last non-missing value on or before the date of the first dose of study drug for Induction Period.

Definition of Baseline for Extension Phase

The Baseline visit date for Extension Phase is the date when the first dose of study drug for Extension Phase is received and referred to as Day 1 or Week 0 of Extension Phase. The Baseline value for a variable is defined as the last non-missing value on or before the date of the first dose of study drug for Extension Phase.

Definition of Rx Days (Days Relative to the First Dose of Study Drug)

Rx Days are calculated for each time point of interest and it provides a quantitative measure of days between the event and the first dose date. That is, the Rx Day is calculated as the event date minus the date of first dose of study drug plus 1.

The Rx Day will be a negative value when the time point of interest is prior to the date of first dose of study drug, and the Rx Day will be a positive value when the time point of interest is after the first dose date. By this calculation algorithm the first dose day is Rx Day 1, while the day prior to the date of first dose is defined as Rx Day –1 (there is no Rx Day 0). Rx Days are used to map actual study visits to the protocol specified study visits.

Dealing with Multiple Measurements Collected on the Same Day

For efficacy related analyses other than imaging endpoints, if multiple measurements for a particular parameter are collected on the same day for the same subject, the average of those measurements will be used.

For safety related analyses, if multiple measurements are made for a particular laboratory or vital sign parameter on the same day for the same subjects, the average of the values will be used in the analyses of change from Baseline. For summaries and listings for shift from baseline and potentially significant values, all collected values within the pre-specified treatment window will be used.

Definition of Analysis Windows

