| Week 12 (Week 28 of the study) | 85 | 2 – 169 |
| Week 36 (Week 52 of the study) | 253 | 170 – 999 |

Rx Day B = date of visit – date of first study drug in double-blind extension phase + 1

a. Day of first dose of study drug in double-blind extension phase.

CD-Related Corticosteroid Use

Subjects not on CD-related corticosteroids (systemic or rectal corticosteroids) at Induction Baseline which are then initiated during the study or who have dosages of these medications increased to greater than the dose taken at Baseline will be censored for efficacy assessments (i.e., will be considered non-responders for categorical endpoints and will have Baseline values carried forward for non-categorical assessments) from that point through the end of the study. These subjects will continue to be evaluated in the safety population.

The equivalent steroid dose will be determined based on the table below:

| Corticosteroid | Equivalent Dose (mg) |
|--------------------|----------------------|
| Cortisone | 25 |
| Hydrocortisone | 20 |
| Prednisone | 5 |
| Prednisolone | 5 |
| Triamcinolone | 4.0 |
| Methylprednisolone | 4.0 |
| Betamethasone | 0.75 |
| Dexamethasone | 0.75 |
| Budesonide | 1 |
| Beclomethasone | 5 |
| Beclometasone | 5 |

Open-Label Therapy

Subjects who are considered by the investigator to have not achieved meaningful symptomatic relief and have met the criteria for inadequate response at or after Week 20 of the study (Week 4 of the Extension Phase) will be eligible to receive open-label therapy with ABT-494 12 mg BID. These subjects will be censored for efficacy assessments (i.e., will be considered non-responders for categorical endpoints and will have the non-missing value prior to open-label therapy carried forward for non-categorical assessments) from that point through the end of the study.

Definition of Missing Data Imputation

The following imputation methods will be used to impute missing values in the efficacy analyses. In addition, an observed case analysis will be performed.

Non-Responder Imputation (NRI)

The NRI approach is used for binary efficacy variables. These variables can take values of 'Achieved' or 'Not Achieved' or may be missing for any reason including discontinuation from study. According to the NRI imputation approach, all missing values will be considered as 'Not Achieved.'

Last Observation Carried Forward (LOCF)

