For all variables (categorical variables and continuous variables), the following rules will be used for the LOCF approach:

1. Extension Baseline and Pre-Baseline values will not be used to impute the missing Post-Baseline values.
2. Missing values after Study Day 1 will be imputed using the latest non-missing values after Day 1 and prior to the missing value. If there are no non-missing values after Baseline, then the LOCF value will be missing.

Observed Case (OC)

Observed case analysis will be performed such that missing values will not be imputed. However, all observed values will be replaced by Induction Baseline value once subjects received CD-related corticosteroid therapy, or value prior to open label therapy once subjects moved to open-label therapy.

Mixed-Effect Model Repeated Measure (MMRM)

The MMRM model will be used for continuous efficacy variables with longitudinal data as the primary analysis. The MMRM model includes the baseline values as covariate, treatment, time point and treatment-by-time point interaction as fixed effects; and subjects within treatment as random effect. An unstructured (co)variance structure will be used to model the within-subject error. The comparison at a time point will be the contrast between treatments at that time point. Satterthwaite's approximation will be used to estimate denominator degrees of freedom.

Imputation of Missing Dates

For Baseline, efficacy, and safety parameters, if the day and/or month are missing, the following conventions will be used to impute the missing dates:

- 01 for missing start day

- End of month for missing end day
- January 1st for missing start month
- December 31st for missing end month

In case of partially missing AE start and stop dates, the dates will be imputed by comparing to first dose date of study medication so that the corresponding AEs will be made treatment-emergent whenever possible. If the start date of an AE is partially missing and the month is the same as the start date of a new therapy, the AE will be made treatment emergent to the new therapy.

In case of missing or partially missing study drug dosing dates, the dates will not be imputed. Subjects will be treated as not receiving dose on that date.

Rule for CDAI Calculation

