- Change from Induction Baseline in fecal calprotectin level over time.
- Change from Induction Baseline in hs-CRP at over time.
- Change from Induction Baseline in IBDQ at Week 52.
- Change from Induction Baseline in EQ-5D at Week 52.
- Change from Induction baseline in EIMs at Week 52.

- Proportion of subjects with isolated ileal Crohn's disease who achieve remission at Week 52.
- Proportion of subjects with isolated ileal Crohn's disease who achieve modified clinical remission at Week 52.

For categorical efficacy endpoints for double-blind extension phase, the pairwise comparisons for the difference in proportions of subjects between ABT-494 3 mg BID group and ABT-494 higher dose groups will be analyzed using the Chi-square test (or Fisher's exact test if $\geq 20\%$ of the cells have expected cell count < 5 .). Additionally, the 95% confidence interval based on normal approximation for the difference in proportions will be provided.

The non-responder imputation will be used for subjects with missing data at the endpoint evaluated. The last observation carried forward (LOCF) method will also be used as the sensitivity analyses.

In general, continuous efficacy variables with repeated measurements will be analyzed using a Mixed Effect Repeated Measure (MMRM) model. The mixed model includes the categorical fixed effects of treatment, week and treatment-by-week interaction and the continuous fixed covariates of Induction baseline measurement. An unstructured variance-covariance matrix will be used. If convergence is not achieved, other variance-covariance matrix will be explored until coverage. The parameter estimations will be based on assumption of data being missing at random and using the method of restrictive maximum likelihood (REML).

Continuous secondary efficacy variables will also be analyzed using an Analysis of Covariance (ANCOVA) model including factors for treatment group, and Induction Baseline values as a covariate. The MMRM analysis is considered primary for inferential purposes.

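### The extension MMRM and ANCOVA adjust for the Induction Baseline only and leave out the Week 16 value at re-randomization, which costs precision on the continuous endpoints

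*SAP*

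**What the plan says.** All references are to the extension SAP unless stated.

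- **Models (Section 10.2).** The MMRM, which is primary for inference, has treatment, week and treatment-by-week as fixed effects, plus "the continuous fixed covariates of Induction baseline measurement". The ANCOVA is described as "including factors for treatment group, and Induction Baseline values as a covariate".
- **General convention (Section 6.0).** "The MMRM model includes the baseline values as covariate", without saying which baseline.
- **Two baselines (Section 6.0).** Besides the Induction Baseline there is an Extension Phase Baseline, the "last non-missing value on or before the date of the first dose of study drug for Extension Phase".
- **How the arms arise (Section 5.2).** "The re-randomization was stratified by dose received during the first 16 weeks", and by overall response at Week 16.
- **Analysis sets (Section 5.1).** "The ITT-R and ITT-NR analysis sets will be used as primary sets for all efficacy analysis". These sets split subjects by Week 16 response, yes or no.
- **Data available.** hs-CRP, fecal calprotectin and IBDQ are scheduled at Week 16 in Table 1. The protocol synopsis lists EQ-5D at Week 16 as well.
- **Open-label switchers (Section 6.0).** For continuous measures they "will have the non-missing value prior to open-label therapy carried forward for non-categorical assessments".

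Protocol Section 8.1.6.2.1 calls for baseline values as a covariate in both models. It does not say which baseline applies to the extension.

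**The concern.** The natural baseline for a randomized comparison is the last measurement before randomization. For the extension that is Week 16. The plan defines and collects this value, then adjusts for one taken before 16 weeks of induction treatment at six different assignments. If Week 16 predicts later values beyond what the Induction Baseline predicts, the models carry avoidable residual variance.

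The MMRM does not recover the information by another route: Tables 2 to 4 place the Week 16 value in the extension baseline window, so it is not one of the repeated responses. Splitting into ITT-R and ITT-NR recovers part of it, but only as a yes/no status built from SES-CD, stool frequency and abdominal pain. The Week 16 hs-CRP, calprotectin, IBDQ and EQ-5D values stay unused.

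For IBDQ the link is partly created by the plan's own rules. No IBDQ is scheduled between Week 16 and Week 52/ET, so a switcher's last scheduled value before open-label therapy is Week 16, and that value becomes the Week 52 outcome.

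**Working it through.** The documents state no power, SD or correlation for the continuous extension endpoints, so there is no plan figure to reproduce. Every correlation below is an assumption.

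**Notation.** r0 = Induction Baseline with outcome; r16 = Week 16 with outcome; r016 = Induction Baseline with Week 16. With the Induction Baseline in the model, analysing the change from it or the later value itself gives the same treatment contrast.

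**1. Gain from adding Week 16, all subjects pooled.**

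Variance cut = (r16 − r0·r016)² / [(1 − r0²)(1 − r016²)]

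- Reference case, r0 = 0.3, r16 = 0.5, r016 = 0.4: (0.5 − 0.12)² / (0.91 × 0.84) = 0.1444 / 0.7644 = 0.189.
- Grid r0 0.2–0.4, r16 0.5–0.7, r016 0.3–0.5. The lowest is at (0.4, 0.5, 0.5): 0.09 / 0.63 = 0.143. The highest is at (0.2, 0.7, 0.5): 0.36 / 0.72 = 0.500.
- SE cut = 1 − √(1 − cut): 7% to 29%. Equivalent extra subjects = 1/(1 − cut) − 1: 17% to 100%.
- Weaker Week 16 correlation over the same r0 and r016: 6–13% at r16 = 0.4 and 2–7% at r16 = 0.3.

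**2. Gain within ITT-R and ITT-NR.** Conditioning on Week 16 response narrows the spread of Week 16 values, so the pooled figures are too high for the primary sets. This was simulated with 2 million draws, r0 = 0.3, r016 = 0.4, responder status correlated 0.3–0.9 with the Week 16 change, and 30–50% responders.

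| r16 | Variance cut | SE cut |
|---|---|---|
| 0.4 | 5–10% | 3–5% |
| 0.5 | 10–18% | 5–10% |
| 0.6 | 18–29% | 9–16% |

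**3. Effect of the carry-forward rules in Section 6.0**, starting from the pooled reference case of 0.189. If a random fraction q of outcomes is replaced by an earlier value, the correlations become weighted averages.

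- *Induction Baseline carried forward (steroid rule).* At q = 0.1, r0 = 0.37 and r16 = 0.49: 0.342² / (0.8631 × 0.84) = 0.161. At q = 0.2, r0 = 0.44 and r16 = 0.48: 0.304² / (0.8064 × 0.84) = 0.136. A simulation of the same rule gave 0.158 and 0.130. The gain falls to about 13–16%.
- *Week 16 IBDQ carried forward (open-label rule).* At q = 0.2, r0 = 0.32 and r16 = 0.60: 0.472² / (0.8976 × 0.84) = 0.295. At q = 0.4, r0 = 0.34 and r16 = 0.70: 0.564² / (0.8844 × 0.84) = 0.428. Simulation gave up to 0.312 and 0.439. The gain rises to about 30–44%.

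**4. Cost of one extra covariate.** With three arms the variance inflates by about 1/(N − 5): 1/15 = 6.7% at N = 20, 1/25 = 4.0% at N = 30, 1/55 = 1.8% at N = 60.

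**5. Bias check.** Simulated two-arm ANCOVA, 8,000 runs, three correlation sets:

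| Scenario | Bias without Week 16 | Bias with Week 16 |
|---|---|---|
| Complete data, 15 or 35 per arm | within 0.004 SD | within 0.004 SD |
| Dropout depends on Week 16 equally in both arms, 35 per arm | within 0.01 SD | within 0.01 SD |
| Dropout depends on Week 16 in one arm only, 35 per arm | 0.06, 0.11, 0.15 SD | about 0 |

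**The case against.** The strongest reply is that this is optional. No bias is alleged, the endpoints are not multiplicity-controlled (Section 10.3), and the only stated power concerns the induction co-primary endpoints. That is fair, and it sets the ceiling on the point.

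Second, the pooled 14–50% does not describe the primary sets. This stands too: the within-set figures should be read first. In a set of 20 with r16 = 0.4, a cut of 5–10% against a 6.7% cost leaves between a 1% loss (0.95 × 1.067 = 1.01) and a 4% gain (0.90 × 1.067 = 0.96).

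Third, the IBDQ figure is largely mechanical, since the covariate equals the outcome for switchers, and the 20–40% switching rate is assumed. Both are true, and the figure is pooled. The residual variance removed is nevertheless real under the plan's rule. The LOCF rule barring Extension Baseline values does not change this: it governs missing values, whereas the open-label rule replaces values after a switch.

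Fourth, the protocol already specifies baseline as the covariate. It does not say which one for the extension, so adding the second does not contradict it.

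Fifth, the Section 6.0 wording is only loose, because Section 10.2 settles it as Induction Baseline. Agreed; aligning the two is a drafting matter.

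Sixth, the four-endpoint scope leaves out the change in EIMs. The SAP does not say that EIMs are a continuous score. If they are modelled as one, the same covariate applies.

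**Conclusion.** The point holds as a low-cost efficiency improvement that should be made. Both extension models omit the pre-randomization value closest to the comparison. Re-randomization balances that value in expectation, and chance imbalance is already reflected in the standard error, so the planned comparison is valid without it for complete data. The exception is dropout that depends on Week 16 differently by arm. IBDQ and EQ-5D are the more exposed there, having a single post-baseline window; earlier extension visits may soften the problem for hs-CRP and calprotectin.

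The likely gain in the primary sets is a 5–29% cut in residual variance for Week 16 correlations of 0.4 to 0.6, or 3–16% in the SE. It may be larger for IBDQ if many subjects switch to open-label therapy, and close to nothing where the set is about 20 subjects and the correlation is weak. Confidence in the size is moderate, because none of the correlations, switching rates or set sizes comes from the documents.

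**What to change.** In extension SAP Section 10.2:

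- Add the Extension Baseline value as a continuous covariate to both the MMRM and the ANCOVA. Keep the Induction Baseline covariate, and keep change from Induction Baseline as the reported endpoint.
- In the MMRM, add the Extension Baseline-by-week interaction for hs-CRP (five extension visits) and calprotectin (two). If the model does not converge, fall back to the main effect, and state whether this comes before or after the existing fallback on the covariance matrix. IBDQ and EQ-5D need only the main effect.
- State the rule for a missing Week 16 value. The Section 6.0 definition already falls back to the last earlier non-missing value, so one sentence confirming this is enough.

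In Section 6.0, name the baselines meant in the MMRM paragraph so that it matches Section 10.2. List the added covariate in Section 12.1.

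The cost is one covariate in text and code. The drawbacks are a few degrees of freedom in small ITT-R and ITT-NR sets, where at about 20 subjects the gain must exceed roughly 7% of variance to pay, and some added convergence risk from the interaction.
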